9.1.1 Adverse (Drug) Reaction

All noxious and unintended responses to a medicinal product related to any dose should be considered an adverse drug reaction. “Responses” to a medicinal product means that a causal relationship between a medicinal product and an adverse event is at least a reasonable possibility, ie, the relationship cannot be ruled out.

9.1.2 Unexpected Adverse Drug Reaction

An Unexpected Adverse Drug Reaction is defined as an adverse reaction, the nature or severity of which is not consistent with the applicable product information.

9.1.3 Assessment of Adverse Events by the Investigator

The Investigator will assess the severity (intensity) of each adverse event as mild, moderate, or severe, and will also categorize each adverse event as to its potential relationship to study drug using the categories of yes/no.

9.1.3.1 Assessment of severity:

Mild – An event that is easily tolerated and generally not interfering with normal daily activities.

Moderate – An event that is sufficiently discomforting to interfere with normal daily activities.

Severe – An event that is incapacitating with inability to work or perform normal daily activities.

9.1.3.2 Causality assessment:

The relationship of an adverse event to the administration of the study drug is to be assessed according to the following definitions:

No (unrelated, not related, no relation) – The time course between the administration of study drug and the occurrence or worsening of the adverse event rules out a causal relationship and another cause (concomitant drugs, therapies, complications, etc.) is suspected.

Yes (related) – The time course between the administration of study drug and the occurrence or worsening of the adverse event is consistent with a causal relationship and no other cause (concomitant drugs, therapies, complications, etc.) can be identified.

The definition implies a reasonable possibility of a causal relationship between the event and the study drug. This means that there are facts (evidence) or arguments to suggest a causal relationship.

The following factors should also be considered:

- The temporal sequence from study drug administration-
 - The event should occur after the study drug is given. The length of time from study drug exposure to event should be evaluated in the clinical context of the event.
- Underlying, concomitant, intercurrent diseases-
 - Each report should be evaluated in the context of the natural history and course of the disease being treated and any other disease the patient may have.
- Concomitant drugs-
 - The other drugs the patient is taking or the treatment the patient receives should be examined to determine whether any of them might be recognized to cause the event in question.
- Known response pattern for this class of study drug-
 - Clinical and/or preclinical data may indicate whether a particular response is likely to be a class effect.
- Exposure to physical and/or mental stresses-
 - The exposure to stress might induce adverse changes in the recipient and provide a logical and better explanation for the event.

- The pharmacology and pharmacokinetics of the study drug-
 - The known pharmacologic properties (absorption, distribution, metabolism, and excretion) of the study drug should be considered.

9.2 Serious Adverse Events

An adverse event or adverse reaction is considered serious if, in the view of either the Investigator or Sponsor, it results in any of the following outcomes:

- Death;
- A life-threatening adverse event;
 - Note: An adverse event or adverse reaction is considered “life-threatening” if, in the view of either the Investigator or Sponsor, its occurrence places the patient at immediate risk of death. It does not include an event that, had it occurred in a more severe form, might have caused death;
- Requires hospitalization or prolongation of existing hospitalizations;
 - Note: Any hospital admission with at least 1 overnight stay will be considered an inpatient hospitalization. An emergency room visit without hospital admission will not be recorded as a SAE under this criterion, nor will hospitalization for a procedure scheduled or planned before signing of informed consent. However, unexpected complications and/or prolongation of hospitalization that occur during elective surgery should be recorded as adverse events and assessed for seriousness. Admission to the hospital for social or situational reasons (ie, no place to stay, live too far away to come for hospital visits) will not be considered inpatient hospitalizations;
- A persistent or significant disability/incapacity or substantial disruption of the ability to conduct normal life functions;
- A congenital anomaly/birth defect; or
- An important medical event.
 - NOTE: Important medical events that may not result in death, be life-threatening, or require hospitalization may be considered an SAE when, based upon appropriate medical judgment, they may jeopardize the patient and may require medical or surgical intervention to prevent one of the outcomes listed above. Examples of such medical events include allergic bronchospasm requiring intensive treatment in an emergency room or at home, blood dyscrasias or convulsions that do not result in inpatient hospitalizations, or the development of drug dependency.

9.3 Serious Adverse Event Reporting – Procedures for Investigators

9.3.1.1 Initial reports

All SAEs occurring from the time of informed consent until 30 days following the last administration of study drug must be reported to [REDACTED] within 24 hours of the knowledge of the occurrence (this refers to any adverse event that meets any of the aforementioned serious criteria). All SAEs that the Investigator considers related to study drug occurring after the 30-day follow-up period must be reported to the Sponsor.

To report the SAE, complete the SAE form electronically in the electronic data capture (EDC) system for the study. When the form is completed, [REDACTED] personnel will be notified electronically and will retrieve the form. If the event meets serious criteria and it is not possible to access the EDC system, send an email to [REDACTED] at [REDACTED] or call the [REDACTED] SAE hotline (phone number listed below), and fax the completed paper SAE form to [REDACTED] (fax number listed below) within 24 hours of awareness. When the EDC system becomes available, the SAE information must be entered within 24 hours of the system becoming available.

9.3.1.2 Follow-up reports

The Investigator must continue to follow the patient until the SAE has subsided or until the condition becomes chronic in nature, stabilizes (in the case of persistent impairment), or the patient dies.

Within 24 hours of receipt of follow-up information, the Investigator must update the SAE form electronically in the EDC system for the study and submit any supporting documentation (eg, patient discharge summary or autopsy reports) to [REDACTED] via fax or e-mail. If it is not possible to access the EDC system, refer to the procedures outlined above for initial reporting of SAEs.

9.4 Pregnancy Reporting

If a patient or female partner of a male patient becomes pregnant during the study or within 30 days of discontinuing study drug, the Investigator should report the pregnancy to [REDACTED] within 24 hours of being notified. [REDACTED] will then forward the Exposure In Utero form to the Investigator for completion.

A patient becoming pregnant while on study drug will immediately be withdrawn from the study and Early Termination study procedures will be performed.

The patient or female partner of a male patient should be followed by the Investigator until completion of the pregnancy. If the pregnancy ends for any reason before the anticipated date, the Investigator should notify [REDACTED]. At the completion of the pregnancy, the Investigator will document the outcome of the pregnancy. If the outcome of the pregnancy meets the criteria for immediate classification as an SAE (ie, postpartum complication, spontaneous abortion, stillbirth, neonatal death, or congenital anomaly), the Investigator should follow the procedures for reporting an SAE.

9.5 Expedited Reporting

The Sponsor will report all relevant information about suspected unexpected serious adverse reactions that are fatal or life-threatening as soon as possible to the FDA, and in any case no later than 7 days after knowledge by the Sponsor of such a case; and that relevant follow-up information will subsequently be communicated within an additional 8 days.

All other suspected unexpected serious adverse reactions will be reported to the FDA as soon as possible but within a maximum of 15 days of first knowledge by the Sponsor.

The Sponsor will also inform all Investigators as required.

9.6 Informed Consent

All patients will be informed of the nature and purpose of the study. Patients will sign informed consent at the Screening Visit (Week -6 to 0), prior to any study procedures being performed.

For patients participating in the extension phase of the study, an informed consent for the Extension Study must be signed prior to any Extension Study-related procedures being performed.

9.7 Demographic Information

Demographic information including day, month, and year of birth; race; ethnicity; and gender will be collected at the Screening Visit (Week -6 to 0).

9.8 Clinical Laboratory Evaluations

All standard blood and urine tests will be performed by a central laboratory. For the purposes of this study, fasting will be defined as nothing by mouth except water for 10 hours. If the patient is not fasting, the Investigator will reschedule the visit as soon as possible but no later than 3 days. Laboratory certification (including expiration date) and normal reference ranges for all laboratories used during the study will be on file with [REDACTED] prior to study initiation. For a complete list of laboratory assessments that will be performed, see Appendix C. For blood sampling procedures, including information on blood volume, collection tubes, sample processing, storage, and shipping, see the Laboratory Manual for this study.

The Investigator must review and sign all laboratory test reports. The Investigator will be notified if laboratory values are outside of normal range and notified of alert values. In this case, the Investigator will be required to conduct clinically appropriate follow-up procedures.

The following analytes will be measured at the Screening Visit (Week -6 to 0), Baseline Visit (Day 1), Main Study Weeks 2, 4, 8, 12, 16, 20, 24, 30, 36 and 38, and the Early Termination Visit, and Extension Study Day 1, Extension Study Weeks 2, 4, 8, 12, 16, 20, 24, 28, 32, 36, and 38, and the Extension Study Early Termination Visit:

- Chemistry – ALP, ALT, amylase, AST, blood urea nitrogen, calcium, carbon dioxide, chloride, creatine kinase, creatinine, direct bilirubin, eGFR (derived from creatinine), [REDACTED] lactate dehydrogenase, lipase, magnesium, phosphate, potassium, serum albumin, sodium, total bilirubin, total protein, and uric acid; and
- Hematology – hemoglobin, hematocrit, red blood cell count, white blood cell count, platelets, mean corpuscular volume, mean corpuscular hemoglobin, and mean corpuscular hemoglobin concentration, red blood cell morphology, % differentials, and absolute differentials.

The following urinalysis analytes will be measured at the Screening Visit (Week -6 to 0), Baseline Visit (Day 1), Main Study Weeks 2, 4, 8, 12, 16, 20, 24, 30, and 36, and the Early Termination Visit, and Extension Study Day 1, Extension Study Weeks 2, 4, 8, 12, 16, 20, 24, 28, 32, 36, and 38, and the Extension Study Early Termination Visit: pH, specific gravity, protein, glucose, ketones, bilirubin, blood, nitrate, urobilinogen, and leukocyte esterase.

Hepatitis B, HepC, and HIV will be measured at the Screening Visit (Week -6 to 0).

Total testosterone, LH, FSH, and estradiol will be measured at the Baseline Visit (Day 1), Main Study Weeks 12, 36, and 38 (Follow-Up Visit), and the Early Termination Visit, and Extension Study Day 1, Weeks 12, 36, and 38 (Follow-Up Visit). Free testosterone to be calculated from

total testosterone, SHBG, and serum albumin for the Baseline Visit (Day 1), Week 12, Week 36, the Follow-Up Visit (Week 38), and the Early Termination Visit.

Sex hormone binding globulin will be measured at the Baseline Visit (Day 1), Main Study Weeks 2, 4, 8, 12, 16, 20, 24, 30, and 36, the Follow-Up Visit (Week 38), and the Early Termination Visit, and Extension Study Day 1, Extension Study Weeks 2, 4, 8, 12, 16, 20, 24, 28, 32, 36, and 38, and the Extension Study Early Termination Visit.

Alkaline phosphatase isoenzymes will be measured at the Baseline Visit (Day 1), Main Study Weeks 12, 36, and 38 (Follow-Up Visit), and the Early Termination Visit, and Extension Study Day 1, Weeks 12, 36, and 38 (Follow-Up Visit).

CKMB and troponin I will be measured at the Baseline Visit (Day 1), Main Study Weeks 2, 4, 8, 12, 16, 20, 24, 30, 36, the Follow-Up Visit (Week 38), and the Early Termination Visit, and Extension Study Day 1, Extension Study Weeks 2, 4, 8, 12, 16, 20, 24, 28, 32, 36, and 38, and the Extension Study Early Termination Visit.

Bile acids will be measured at Baseline Visit (Day 1), Main Study Weeks 2, 12, and 36, and the Early Termination Visit, and Extension Study Day 1, Extension Study Weeks 2, 12, and 36, and the Extension Study Early Termination Visit.

Urine pregnancy tests will be administered for women of child bearing potential only at the Baseline Visit (Day 1), Main Study Weeks 2, 4, 8, 12, 16, 20, 24, 30, and 36, and the Early Termination Visit, and Extension Study Day 1, Extension Study Weeks 2, 4, 8, 12, 16, 20, 24, 28, 32, and 36 and the Extension Study Early Termination Visit. Serum pregnancy tests will be administered at the Screening Visit (Week -6 to 0) for women of child bearing potential only.

Thyroid axis hormones (T4, FT4, total T3, free T3 [FT3], and TSH) will be measured at the Screening Visit (Week -6 to 0), the Baseline Visit (Day 1), Weeks 2, 4, 8, 12, 16, 20, 24, 30, and 36, the Follow-Up Visit (Week 38), and the Early Termination Visit, and Extension Study Day 1, Extension Study Weeks 2, 4, 8, 12, 16, 20, 24, 28, 32, and 36 and the Extension Study Early Termination Visit. Anti-thyroid peroxidase antibodies will be measured at the Baseline Visit (Day 1). Thyroxine-binding globulin will be measured at the Baseline Visit (Day 1), Weeks 2, 4, 8, 12, 16, 20, 24, 30, and 36, the Follow Up Visit (Week 38), and the Early Termination Visit, and Extension Study Day 1, Extension Study Weeks, 2, 4, 8, 12, 16, 20, 24, 28, 32, and 36 and the Extension Study Early Termination Visit if necessary. Reverse T3 will be measured at the Baseline Visit (Day 1), Week 12, Week 36 and the Early Termination Visit, and Extension Study Day 1, Extension Study Weeks 2, 12, and 36, and the Extension Study Early Termination Visit.

A fasting metabolic panel ([REDACTED]) will be measured at the Screening Visit (Weeks -6 to 0), the Baseline Visit (Day 1), Week 12, Week 36, and the Early Termination Visit, and Extension Study Day 1, Extension Study Weeks 12 and 36, and the Extension Study Early Termination Visit if necessary. [REDACTED] will be measured at the Baseline Visit (Day 1), Week 12, Week 36, and the Early Termination Visit, and Extension Study Day 1, Extension Study Weeks 12 and 36, and the Extension Study Early Termination Visit.

Fasting lipid parameters (triglyceride, total cholesterol, LDL-C (direct and calculated), HDL-C, and non-HDL-C) will be collected at the Screening Visit (Weeks -6 to 0), the Baseline Visit (Day 1), Main Study Weeks 2, 4, 8, 12, 16, 20, 24, 30, and 36, the Follow-Up Visit (Week 38), and the Early Termination Visit, and Extension Study Day 1, Extension Study Weeks, 2, 4, 8, 12, 16, 20,

24, 28, 32, and 36 and the Extension Study Early Termination Visit. ApoB, Apo A1 and Lp(a) particles will be collected at the Baseline Visit (Day 1), Main Study Weeks 2, 4, 8, 12, 16, 20, 24, 30, and 36, the Follow-Up Visit (Week 38), and the Early Termination Visit, and Extension Study Day 1, Extension Study Weeks 2, 4, 8, 12, 16, 20, 24, 28, 32, and 36 and the Extension Study Early Termination Visit.

Cytokeratin-18, FIB-4, ELF, fibrinogen, haptoglobin, alpha-2 macroglobulin, N-terminal pro b-type natriuretic peptide, apolipoprotein C-III, and ferritin will be measured at the Baseline Visit (Day 1), Week 12, Week 36, and the Early Termination Visit, and Extension Study Day 1, Extension Study Weeks 12 and 36, and the Extension Study Early Termination Visit.

High-sensitivity C-reactive protein will be measured at the Baseline Visit (Day 1), Weeks 4, 12, 24, and 36, and the Early Termination Visit, and Extension Study Day 1, Extension Study Weeks 4, 12, 24, and 36, and the Extension Study Early Termination Visit.

Bone biomarkers Type 1 procollagen N-terminal propeptide and CTX will be measured at the Baseline Visit (Day 1), Main Study Weeks 12 and 36, and the Early Termination Visit, and Extension Study Day 1, Extension Study Weeks 12 and 36, and the Extension Study Early Termination Visit.

Pre-dose PK samples will be drawn at baseline (Day 1), Main Study Weeks 2, 8, 16, 24, and 36, and the Early Termination Visit, and Extension Study Day 1, Extension Study Weeks 2, 4, 8, 16, 24, and 36, and the Extension Study Early Termination Visit. In addition, postdose PK samples will be collected at Main Study Week 2 as described in 6.4.2 and the Extension Study Week 2 as described in 6.7.2.

Coagulation markers (APTT, PT, and INR) will be measured at the Screening Visit (Week -6 to 0), the Baseline Visit (Day 1), Weeks 2, 4, 8, 12, 16, 20, 24, 30, and 36, at the Follow-Up Visit (Week 38), and at the Early Termination Visit, and Extension Study Day 1, Extension Study Weeks 2, 4, 8, 12, 16, 20, 24, 28, 32, and 36 and the Extension Study Early Termination Visit.

Genomic samples will be drawn at the Baseline Visit (Day 1).

9.9 Vital Signs and Anthropometrics

Vital signs and anthropometrics (weight, BMI, waist circumference, waist-hip ratio, temperature, pulse [resting], respiratory rate, and seated blood pressure [resting]) will be measured at the Screening Visit (Week -6 to 0), the Baseline Visit (Day 1), Main Study Weeks 2, 4, 8, 12, 16, 20, 24, 30, and 36, and the Early Termination Visit, and Extension Study Day 1, Extension Study Weeks 2, 4, 8, 12, 16, 20, 24, 28, 32, and 36 and the Extension Study Early Termination Visit.

Blood pressure will be measured using a standardized process:

- Patient will sit for 5 minutes with feet flat on the floor and measurement arm supported so that the midpoint of the manometer cuff is at heart level;
- Site staff will use of a mercury sphygmomanometer or automatic blood pressure device with an appropriately sized cuff with the bladder centered over the brachial artery;
- Site staff will record the arm used for measurement and use the same arm throughout the study; and
- Site staff will measure and record the blood pressure.

Blood pressure will be recorded to the nearest 2 mmHg mark on the manometer or to the nearest whole number on the automatic device. A blood pressure reading will be repeated 1 to 2 minutes later, and the second reading will also be recorded to the nearest 2 mmHg mark.

9.10 Electrocardiograms

Twelve-lead ECGs with rhythm strip will be performed at the Screening Visit (Week -6 to 0), the Baseline Visit (Day 1), Main Study Weeks 2, 4, 8, 12, 16, 20, 24, 30, and 36, and the Early Termination Visit, and Extension Study Day 1, Extension Study Weeks 2, 4, 8, 12, 16, 20, 24, 28, 32, and 36 and the Extension Study Early Termination Visit. Twelve-lead ECGs will be performed in triplicate in a consecutive manner after the patient has been resting in the supine position for at least 10 minutes. The ECG will include 12 standard leads and will be recorded at a paper speed of 25 mm/sec. The following ECG parameters will be recorded:

- PR interval,
- QRS interval,
- Heart rate,
- RR interval,
- QT interval,
- QTcB interval, and
- QTcF interval.

All ECGs must be evaluated by a qualified reader for the presence of abnormalities.

9.11 Physical Examinations

A complete physical examination will include documentation of general appearance, skin, and specific head and neck, heart, lung, abdomen, extremities, and neuromuscular assessments. A complete physical examination will be performed at the Screening Visit (Week -6 to 0), and a symptom-directed physical examination will be completed at the Baseline Visit (Day 1), Main Study Weeks 2, 4, 8, 12, 16, 20, 24, 30, and 36, and the Early Termination Visit, and Extension Study Day 1, Extension Study Weeks 2, 4, 8, 12, 16, 20, 24, 28, 32, and 36 and the Extension Study Early Termination Visit.

9.12 Diet and Lifestyle Counseling

Patients will be counseled on maintaining a consistent diet, exercise regimen, and lifestyle at the Screening Visit (Week -6 to 0), Baseline Visit (Day 1), and Main Study Weeks 2, 4, 8, 12, 16, 20, 24, 30, and 36, and Extension Study Day 1 and Weeks 2, 4, 8, 12, 16, 20, 24, 28, 32, and 36.

9.13 Health-Related Assessment-Quality of Life

Patients will undergo a HR-QoL SF-36 assessment at the Baseline Visit (Day 1), Weeks 4, 12, 24, and 36, and the Early Termination Visit, and Extension Study Day 1, Extension Study Weeks 4, 12, 24, and 36 and the Extension Study Early Termination Visit.

9.14 Proton Density Fat Fraction Magnetic Resonance Imaging

Patients will undergo MRI-PDFF at the Screening Visit (Week -6 to 0), Main Study Weeks 12 and 36, and the Early Termination Visit, and Extension Study Weeks 12 and 36 and the Extension Study Early Termination Visit. The Screening Visit MRI-PDFF will be used as baseline and should be obtained as close to randomization as possible. The MRI-PDFFs will be read by a central reader.

9.15 Liver Biopsy

Patients will undergo liver biopsy at the Screening Visit (Week -6 to 0) only in the event that the patient does not have available liver biopsy within 180 days of randomization. If a historical biopsy is to be used, patients must have had no change in metabolic status (diabetes, lipid metabolism, and/or >5% weight gain or loss) or change in diabetes medications. If a historical biopsy is not available, patients must have confirmation of $\geq 10\%$ liver fat content on MRI-PDFF prior to undergoing liver biopsy. However, if, in the opinion of the patient's physician, the patient would benefit from and be advised to obtain a liver biopsy, the patient may undergo liver biopsy prior to MRI-PDFF. All patients will undergo liver biopsy at Week 36. Patients may undergo liver biopsy at the Early Termination Visit based on the discretion of the Investigator. Liver biopsies will be read by 1 central reader. Reading will include assessment of fibrosis stage, portal inflammation, and NAS.

9.16 Dual-Energy X-Ray Absorptiometry

Patients will undergo DXA scan to assess bone mineral density at the Baseline Visit (Day 1), Main Study Week 36, and the Early Termination Visit, and Extension Study Week 36 and the Extension Study Early Termination Visit.

9.17 Drug Induced Liver Injury Monitoring

Close clinical monitoring must be applied to the following:

- Any patient who had normal baseline ALT, AST, and total bilirubin values and then experienced a newly treatment-emergent ALT and/or AST value $>3 \times$ ULN OR total bilirubin value $>2 \times$ ULN; or
- Any patient who had elevated ALT, AST, or total bilirubin values at baseline and then experienced a 2-fold increase above the baseline ALT and/or AST values AND/OR a 1.5-fold increase above the baseline total bilirubin values.

The patient must return to the study site within 48 to 72 hours for a confirmatory evaluation and central laboratory testing. Repeat laboratory analyses must include the following chemistries: ALP, ALT, AST, total and direct bilirubin, INR and lactate dehydrogenase. At the same time repeat samples are drawn, a PK sample must be taken.

Close monitoring of study patients includes:

- Repeating liver enzyme and serum bilirubin tests at least once a week if abnormalities stabilize and the patient is asymptomatic;
- Obtaining a more detailed history of symptoms and prior or concomitant diseases;

- Obtaining a history of concomitant drug use (including non-prescription medications and herbal and dietary supplement preparations), alcohol use, recreational drug use, and special diets;
- Ruling out acute viral hepatitis Types A, B, C, D, and E; autoimmune or alcoholic hepatitis; hypoxic/ischemic hepatopathy; and biliary tract disease;
- Obtaining a history of exposure to environmental chemical agents;
- Considering gastroenterology or hepatology consultation; and
- Reporting to the Sponsor and Medical Monitor within 48 hours.

If close monitoring is not possible, study drug should be discontinued. If a patient lives in a remote area, they can be tested locally and the results communicated to the investigator site promptly.

Study drug must be discontinued if any of the following criteria are met:

- For patients with ALT and/or AST values $\leq 1.5 \times$ ULN at baseline:
 - Post-baseline ALT or AST value is $> 5 \times$ ULN, or
 - Post-baseline ALT or AST value is $> 3 \times$ ULN and total bilirubin is $> 2 \times$ ULN or INR is > 1.5 ;
- For patients with ALT and/or AST values $> 1.5 \times$ ULN at baseline:
 - Post-baseline ALT or AST value is $> 3 \times$ the baseline value and at least $5 \times$ ULN, or
 - Post-baseline ALT or AST value is $> 2 \times$ the baseline value and is accompanied by a concomitant total bilirubin increase to $> 2 \times$ the baseline value or the INR concomitantly increases by > 0.2 .

Study drug will be discontinued for any patient with the appearance of fatigue, nausea, vomiting, right upper quadrant pain or tenderness, fever, rash, and/or eosinophilia ($> 5\%$) and 1 of the following:

- Had normal baseline ALT and AST values and then experienced a $> 3 \times$ ULN post-baseline increase; or
- Had elevated ALT and/or AST levels at baseline and then experienced a 2-fold post-baseline increase.

Study drug may be resumed once the toxicity returns to below the values prompting discontinuation. If total bilirubin, ALT, or AST elevation recurs following rechallenge with study drug, then study drug must be permanently discontinued and the patient managed according to local practice.

If acute viral hepatitis is diagnosed while the patient is on the study, study drug must be discontinued immediately and the necessary Early Termination Visit assessments will be performed (see Section 6.6).

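### After an enzyme-only liver stop, Section 9.17 lets drug restart just below the stopping level, with no recovery margin, at up to 1.67 times its own close-monitoring level for normal baselines

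*Protocol*

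**What the plan says.** Protocol Section 9.17 works in three layers.

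- **Close monitoring.** With normal baseline ALT, AST and bilirubin, the enzyme trigger is a "newly treatment-emergent ALT and/or AST value $>3 \times$ ULN". With a raised baseline, it applies to a patient who had raised values "and then experienced a 2-fold increase above the baseline ALT and/or AST values". The response includes this step: "The patient must return to the study site within 48 to 72 hours for a confirmatory evaluation and central laboratory testing". A PK sample, weekly tests, exclusion of other causes and a report to the Sponsor and Medical Monitor within 48 hours are also listed.
- **Mandatory stop.** On enzymes alone, the limit is above 5 x ULN for baselines up to 1.5 x ULN. For higher baselines the stop applies when the value "is $> 3 \times$ the baseline value and at least $5 \times$ ULN". Lower enzyme values also stop drug in combination: above 3 x ULN when "total bilirubin is $> 2 \times$ ULN or INR is > 1.5" (baseline up to 1.5 x ULN), or, for higher baselines, when the enzyme "is $> 2 \times$ the baseline value and is accompanied by a concomitant total bilirubin increase" or an INR rise above 0.2. Listed symptoms also stop drug at roughly the monitoring level; for raised baselines the wording is "Had elevated ALT and/or AST levels at baseline and then experienced a 2-fold post-baseline increase".
- **Restart.** "Study drug may be resumed once the toxicity returns to below the values prompting discontinuation". A renewed elevation after rechallenge means permanent discontinuation.

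The liver section of the synopsis repeats only the monitoring triggers. Neither Section 4.3 (withdrawal) nor Section 10.2.4 (DSMB) sets a lower restart level.

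**The concern.** A mandatory stop is the strongest action 9.17 takes, yet a small fall back across the same line undoes it. Drug may then be given again while enzymes are still in the range where 9.17 requires close monitoring for drug-induced liver injury.

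The main safeguard after restart is the permanent stop on recurrence. It needs a first episode that has ended. If drug restarts at 4.9 x ULN and the next value is 5.2 x ULN, the text does not say whether this is recurrence or the first episode continuing, and no level is attached to the word. Section 6.7 also points to 9.17 for the extension, whose entry criteria (Inclusion #9) select patients with persistently raised enzymes.

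**Working it through.** The plan states no figure for a recovery margin, so the check compares the thresholds in 9.17 with each other.

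**Inputs.** Let b be the baseline enzyme in multiples of ULN. The ALT ULN is 41 U/L (Exclusion #15, which also caps entry at 5 x ULN). The values prompting discontinuation are read as the thresholds. If they meant the patient's own measured value, restart could occur higher still, so this reading is the conservative one.

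**Formulas, in x ULN.**
- Enzyme-only stop, and so the restart ceiling: S = 5 if b ≤ 1.5; otherwise S = max(5, 3b). The two arms cross at b = 5/3 = 1.67.
- Close-monitoring level: M = 3 if baseline is normal. If raised, M = 2b (reading A, two-fold means 2 x baseline) or M = 3b (reading B, an increase of twice the baseline on top of it).

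**Results.** Levels are ALT in U/L, that is, the multiple times 41.

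| Baseline b | Restart ceiling S | M, reading A | S/M, A | M, reading B | S/M, B |
|---|---|---|---|---|---|
| 1.0 (normal) | 205 | 123 | 1.67 | 123 | 1.67 |
| 1.01 | 205 | 83 | 2.48 | 124 | 1.65 |
| 1.2 | 205 | 98 | 2.08 | 148 | 1.39 |
| 1.5 | 205 | 123 | 1.67 | 184.5 | 1.11 |
| 2 | 246 | 164 | 1.50 | 246 | 1.00 |
| 3 | 369 | 246 | 1.50 | 369 | 1.00 |
| 5 | 615 | 410 | 1.50 | 615 | 1.00 |

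For raised baselines the range is 1.5 to 2.5 under A and 1.0 to 1.67 under B. The normal-baseline ratio of 5/3 = 1.67 does not depend on the reading.

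**Which reading fits 9.17 better.** For baselines above 1.5 x ULN, the combined stop uses 2 x baseline for the enzyme and 2 x baseline for bilirubin. Under B, monitoring would start at 3 x and 2.5 x baseline, above those stop levels (2/3 = 0.67 and 2/2.5 = 0.80). Under A the ratios are 2/2 = 1.00 and 2/1.5 = 1.33, so monitoring starts at or below the stop. A is the more coherent reading, but the text allows both.

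**Where the enzyme gap is small or absent.** After a combined stop, the enzyme part of the restart level under reading A equals the monitoring level for normal baselines (3/3 = 1.00) and for baselines above 1.5 x ULN (2b/2b = 1.00). Between 1 and 1.5 x ULN it is 3/(2b), falling from about 1.5 to 1.00. After a symptom stop it is already about the monitoring level, although nothing requires the symptoms to have resolved.

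**The case against.** The strongest reply is that 9.17 already permits dosing between the monitoring and stop levels. A never-stopped, asymptomatic patient at 4.5 x ULN stays on drug under weekly tests, and drug is withdrawn there only if close monitoring is not possible. A restarted patient at 4.5 x ULN enters the same regime. This stands. A reader might infer that 9.17 contradicts itself, and the documents do not support that.

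The affected group is also narrow. The symptom rule and the combined bilirubin/INR stops still apply in this range, so what remains is essentially asymptomatic patients without stop-level bilirubin or INR. Restart is permissive, a new crossing of the threshold stops drug again, the Investigator may withdraw the patient (Section 4.3), and the DSMB reviews liver events. These points stand too.

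A reader might also infer that no restart level exists at all. One does exist: it is the stop level. What is missing is a margin below it.

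The reply does not dispose of the point, because none of these controls sets a lower level to reach before re-exposure. The recurrence rule needs that lower level to be workable.

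**Conclusion.** The point holds as a safety-design weakness of modest size. After an enzyme-only stop the restart ceiling equals the stop level, 1.67 times the close-monitoring level for normal baselines. For raised baselines the ratio depends on how the two-fold trigger is read, as tabulated.

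The figure of 2.5 should not be taken as typical. It needs reading A and a baseline barely above 1 x ULN; from 1.67 x ULN upward the ratio is 1.50 under A, and there is no enzyme gap under B.

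The ratios assume that the rising enzyme decides which monitoring bullet applies. The first bullet requires ALT, AST and bilirubin all to be normal at baseline. If the rising enzyme was normal but another marker was raised, the second bullet applies and the ratio is larger: at b = 0.8, 5/1.6 = 3.1 under A or 5/2.4 = 2.1 under B.

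A reader might infer that patients were harmed, or that the cardiovascular restart rule in Section 9.18 (return to normal or baseline) is the standard to copy. Neither follows. The documents give no rate of liver stops, so the number affected is unknown and probably small. Section 9.18 has lower triggers and shows only that the protocol sets a recovery level elsewhere.

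**What to change.** Replace the restart sentence in 9.17 with:

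> Study drug may be resumed only when, on a repeat test, ALT and AST are each below the greater of 3 x ULN and 2 x that enzyme's baseline value, total bilirubin and INR no longer meet any discontinuation criterion of this section, and any symptoms that prompted discontinuation have resolved.

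Keep the permanent-stop rule for recurrence. In the raised-baseline monitoring bullet, replace the two-fold and 1.5-fold wording with: a value >2 x baseline ALT and/or AST and/or >1.5 x baseline total bilirubin.

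The new ceiling is R = max(3, 2b). It is 123 U/L for b up to 1.5, against 205 now (3/5 = 0.60 of the stop level), and two-thirds of the stop level from b = 1.67 upward (2b/3b). Taking the greater of the two limits for each enzyme avoids forcing a patient with one raised marker to bring the other enzyme within the normal range, and avoids a jump at 1 x ULN. In exchange, baselines between 1 and 1.5 x ULN may still restart somewhat above the reading-A monitoring level, under continued close monitoring. INR is held to 9.17's own limits; requiring a return to baseline could block restart after an ALT-only stop.

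The cost is one sentence, one clarified trigger, and somewhat longer drug interruptions in a few patients.
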